2.1.2 Full Analysis Set for Live Births Intended for Postnatal Treatment

All enrolled fetuses that have satisfied inclusion/exclusion criteria and belong to FAV 1+2 and no-FAV 1+2 groups and not listed as the high-risk population above that also are live at birth will be included in the Full Analysis Set at birth (FAS_{BIRTH}) population. Infants wrongly included in the study will not be part of the FAS_{BIRTH} population, but will be described in the safety analyses.

2.1.3 Per-Protocol Population for All Enrolled

All enrolled fetuses with no major protocol violations will be included in the Per Protocol enrolled (PP_{ENR}) population. The final decisions regarding the PP_{ENR} population will be taken at the Clean File meeting before the database lock.

2.1.4 Per-Protocol Population for Live Births Intended for Postnatal Treatment

All enrolled fetuses that are *live at birth and intended for treatment* with no major protocol violations will be included in the Per Protocol at birth (PP_{BIRTH}) population. The final decisions

Statistical Analysis Plan

Protocol No:

regarding the PP_{BIRTH} population will be taken at the Clean File meeting before the database lock.

2.1.5 High-Risk Population

The high-risk population will include all subjects with any of the following conditions at inclusion: Severe MR and severe LA enlargement and/or intact or highly restrictive inter-atrial communication and/or hydrops. Fetuses developing any of these conditions after inclusion will not be analysed as belonging to the high-risk population.

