#### **Inclusion criteria**

The inclusion criteria will be identical in the intervention and the non-intervention cohorts. A modification of the inclusion criteria published by the group in Boston (2) and by the group in Linz (3) will be used. The modification is based on the retrospective study (9,10) and represent the currently used criteria for intervention.

- A. All of the following echocardiographic criteria need to be satisfied between 23+0 and 31+6 weeks (z-scores according to Schneider et al (13)):
- 1. Aortic valve stenosis with antegrade flow through the valve
- 2. Predominantly left-to-right shunt at the atrial level

- 3. Predominantly retrograde flow in the aortic arch between the first two brachiocephalic vessels
- 4. Qualitatively depressed left ventricular function
- 5. LV end-diastolic diameter Z-score  $> \pm 0$
- 6. Left ventricular inlet length in diastole :
  - a. Gest age  $\leq 24+6$ : Z-score  $> \pm 0$
  - b. Gest age 25+0 to 27+6: Z-score > -0.75
  - c. Gest age  $\geq 28+0$ : Z-score > -1.50
- 7. Mitral valve diameter in diastole Z-score > -2.0
- B. All of the following postnatal treatment options need to be available:
  - 1. Surgical or catheter based aortic valvotomy
  - 2. Ross-Konno surgery
  - 3. Norwood or hybrid stage-one surgery

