#### **Exclusion criteria**

- 1. Any associated cardiac defect except persistent left superior vena cava and coarctation of the aorta
- Any significant (i.e. that might influence outcome) extracardiac anomaly and/or known chromosomal aberration. Also, if such a condition is present at inclusion but diagnosed only after birth the case will be retrospectively excluded.

Endocardial fibroelastosis is accepted. Cases with severe mitral regurgitation and left atrial enlargement with or without restrictive or intact atrial communication and with or without hydrops will be included but analyzed as a separate group (17). Also cases with atrial septal balloon dilatation or stent placement will be included if the first intervention was aortic valvuloplasty or if no fetal aortic valvuloplasty was performed.

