## Electronic case report forms (eCRF)

There are 14 eCRF's:

1. eCRF Inclusion criteria

All inclusion and no exclusion criteria need to be satisfied for a case to be included.

2. eCRF Inclusion

Include case if inclusin/exclusion criteria satisfied.

3. eCRF Counselling on fetal aortic valvuloplasty

If councelling was performed and, if so, what the decision was.

4. eCRF Baseline fetal echo 23+0 - 31+6

The baseline fetal echo is performed between 23+0 and 31+6 weeks. If an intervention is performed, the last exam before the intervention should be used as baseline fetal echo.

5. eCRF Additional baseline fetal echo 23+0 - 31+6

In case there is a late descision to perform an intervention, after a baseline fetal echo has already been submitted, there is an option to add an additional baseline fetal echo in the system.

6. eCRF Fetal interventions

A new eCRF Fetal interventions should be added for each intervention performed.

7. eCRF Follow-up fetal echo 33+0 - 34+6

The follow-up fetal echo is performed between 33+0 and 34+6 weeks.

8. eCRF Neonatal - Birth

Gestational age and size at birth, mode of delivery and pharmacological support.

9. eCRF Neonatal - Echo

First full study after birth, and before the first postnatal intervention, surgery or cath (except emergency atrial septostomy)

10. eCRF Neonatal - Cardiac clinical diagnosis

Cardiac diagnoses before the first intervention, surgery or cath (except emergency atrial septostomy)

11. eCRF Neonatal - Neonatal discharge

Type of circulation and clinical diagnoses at discharge.

12. eCRF Follow-up at 2 years of age

Type of circulation, clinical diagnoses, pulmonary hypertension, neurological sequealae, somatic growth.

13. eCRF Postnatal procedures

All cardiac surgical and catheter interventional procedures from birth to 2 years follow-up

14. eCRF Subject termination

Reason for subject termination including completion at 2 years of age.

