1.3 Inclusion and Exclusion Criteria

1.3.1 Inclusion Criteria

Inclusion criteria represent currently used criteria for fetal intervention in aortic stenosis. They are identical in the intervention and the non-intervention groups.

Protocol

Statistical Analysis Plan

Effect of fetal aortic valvuloplasty on outcomes

Protocol No:

1.0

A. All of the following echocardiographic criteria need to be satisfied between 23+0 and 31+6 weeks (z-scores* according to schneider):

- 1 Aortic valve stenosis with antegrade flow through the valve
- 2 Predominantly left-to-right shunt at the atrial level
- 3 Predominantly retrograde flow in the aortic arch between the first two brachiocephalic vessels
- 4 Qualitatively depressed left ventricular function
- 5 LV end-diastolic diameter z-score* > +/-0
- 6 Left ventricular inlet length in diastole, z-score* according to gestational age
 - a. GA ≤ 24+6: Z-score > ±0
 - b. GA 25+0 to 27+6: Z-score > -0.75
 - c. $GA \ge 28+0$: Z-score > -1.50
- 7 Mitral valve diameter in diastole z-score* > -2.0
- B. All of the following postnatal treatment options need to be available:
- 1 Surgical or catheter based aortic valvotomy
- 2 Ross-Konno surgery
- 3 Norwood or hybrid stage-one surgery

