2 STUDY POPULATIONS

2.1 Definition of Study Populations

2.1.1 Full Analysis Set for All Enrolled

Fetuses with severe MR and severe LA enlargement and/or intact or highly restrictive interatrial communication and/or cases with hydrops present at inclusion are all high-risk cases regarding survival, but may have a rather good prognosis if they survive the first critical period. It is likely they will be overrepresented in the FAV group to such a degree that it will be difficult to control for through propensity score matching. Therefore this subpopulation will be excluded from the full analysis set and analysed separately. Fetuses developing any of these conditions after inclusion will not be excluded from the full analysis set.

All enrolled fetuses that have satisfied inclusion/exclusion criteria and belong to FAV 1+2 and no-FAV 1+2 groups and not listed as belonging to the high-risk population described above will be included in the Full Analysis Set enrolled (FAS_{ENR}) population. Infants wrongly included in the study (not fulfilling all inclusion or fulfilling any of the exclusion criteria) will not be part of the FAS_{ENR} population, but will be described in the safety analyses. As detailed under 1.3.2, also subjects with exclusion criteria present at inclusion but diagnosed only after birth will be retrospectively excluded from the FAS_{ENR} population.

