4.6.3 Subgroup Analyses

Descriptive data on primary and secondary outcomes will be performed on following subgroups for FAV 1+2 vs no-FAV 1+2, FASENR and FASBIRTH populations:

- Subgroup 1: Fetuses with diagnosis of fetal aortic stenosis that undergo technically . successful FAV and additional fetal cardiac intervention(s) such as atrial septal balloon dilatation or stent placement.
- Subgroup 2 (part of the High-risk population): Fetuses with diagnosis of fetal aortic stenosis and hydrops.
- Subgroup 3 (equals to High-risk population): Fetuses with diagnosis of fetal aortic stenosis, severe mitral regurgitation and left atrial enlargement with or without restrictive or intact atrial communication and with or without hydrops.

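### The high-risk group has conflicting definitions, its subgroup tables are placed on populations that exclude it, and an intact septum cannot literally meet inclusion criterion A2

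*SAP*

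**What the plan says.** **Removal from the main analysis.** SAP 2.1.1 names a set of high-risk fetuses and says: "Therefore this subpopulation will be excluded from the full analysis set and analysed separately". SAP 2.1.5 defines the set. It opens with "The high-risk population will include all subjects with any of the following conditions at inclusion" and lists "Severe MR and severe LA enlargement and/or intact or highly restrictive inter-atrial communication and/or hydrops". SAP 2.1.2 applies the same removal to FAS_BIRTH. Fetuses that develop one of these conditions only after inclusion stay in the full analysis set.

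**The Protocol's separate group.** Protocol, Exclusion criteria, says that cases with severe MR and LA enlargement, "with or without restrictive or intact atrial communication and with or without hydrops will be included but analyzed as a separate group". Subgroup c under Protocol, Data analysis and statistical support, is built the same way.

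**The SAP subgroup.** SAP 4.6.3 has "Subgroup 3 (equals to High-risk population): Fetuses with diagnosis of fetal aortic stenosis, severe mitral regurgitation and left atrial enlargement", then adds septal restriction and hydrops as optional features. Subgroup 2 is hydrops and is described as part of the high-risk population. The opening sentence of 4.6.3 places all subgroups on FAS_ENR and FAS_BIRTH. The titles of Tables 2.4.1.2, 2.4.1.3, 2.4.2.2 and 2.4.2.3 do the same.

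**Entry.** Criterion A2 in both documents is "Predominantly left-to-right shunt at the atrial level". SAP 1.3.1 says "All of the following echocardiographic criteria need to be satisfied between 23+0 and 31+6 weeks", and Protocol, Electronic case report forms, says "All inclusion and no exclusion criteria need to be satisfied for a case to be included".

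**The concern.** The high-risk definition decides who leaves the confirmatory comparison. SAP 2.1.1 itself expects these fetuses to have poor early survival and to be overrepresented in the FAV group, so the boundary matters in a non-randomised comparison of about 100 against 50. Three things do not fit together.

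1. SAP 2.1.5 treats each condition as sufficient. The Protocol text and the Subgroup 3 text treat severe MR with LA enlargement as necessary.
2. The separate analysis promised in SAP 2.1.1 is assigned to populations from which its subjects have been taken out.
3. Both documents provide for enrolled fetuses with an intact septum, but the entry criteria, read literally, do not admit them.

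If this is left open, the programmer has to choose a definition and a population. If that choice is made after outcomes are known, it can be criticised whichever way it goes.

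**Working it through.** The plan gives no figure on this point, and its power calculations do not enter. The check is one of set membership.

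**Step 1: list the combinations.** SAP 2.1.5 has three conditions: (M) severe MR with severe LA enlargement; (S) intact or highly restrictive septum; (H) hydrops. The non-empty combinations number 2 × 2 × 2 − 1 = 7.

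| M | S | H | High-risk under SAP 2.1.5 | Fits Subgroup 2 text | Fits Subgroup 3 text |
|---|---|---|---|---|---|
| yes | no | no | yes | no | yes |
| yes | yes | no | yes | no | yes |
| yes | no | yes | yes | yes | yes |
| yes | yes | yes | yes | yes | yes |
| no | yes | no | yes | **no** | **no** |
| no | no | yes | yes | yes | **no** |
| no | yes | yes | yes | yes | **no** |

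All seven leave FAS_ENR. Four fit the Subgroup 3 text. Septum alone, hydrops alone, and septum with hydrops do not. Septum alone fits neither subgroup text, so only the Subgroup 3 label covers it.

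**Step 2: check the other direction.** SAP 2.1.5 asks for severe LA enlargement; the Protocol and Subgroup 3 texts ask only for LA enlargement. A fetus with severe MR, non-severe LA enlargement, an open septum and no hydrops fits the Subgroup 3 text but stays in FAS_ENR. The texts also differ between highly restrictive and restrictive. That difference does not by itself change who fits Subgroup 3, because the septum is optional there. So neither set contains the other.

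**Step 3: apply the stated population.** SAP 2.1.1 and 2.1.2 remove every high-risk fetus from FAS_ENR and FAS_BIRTH. Tabulating Subgroups 2 and 3 on those sets leaves 0 of the 7 combinations. The tables need not be blank: the Step 2 fetus, or one whose hydrops developed after inclusion, could fit the subgroup text. They would, however, contain no high-risk subject. No efficacy table in SAP section 7.1 names the high-risk population.

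Subgroup 3 therefore covers 7 of 7 by label, 4 of 7 by text and 0 of 7 by stated population.

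**Step 4: compare with A2.** Splitting the septum into open, restrictive and intact gives 2 × 3 × 2 = 12 profiles, of which 11 are high-risk. Four of the 12 have an intact septum (2 × 2). With no communication there is no atrial shunt in either direction, so all four fail A2 as written. The four restrictive profiles can meet it. Yet SAP 2.1.5 lists an intact septum as a high-risk condition, and Protocol, Exclusion criteria, accepts it in cases that also have severe MR and LA enlargement. Under SAP 2.1.1 an enrolled intact-septum fetus is either an erroneous inclusion, described only with safety, or a high-risk case, analysed separately. It is outside FAS_ENR on both readings.

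**The case against.** It can fairly be said that the SAP is clear where it counts. The removal rule is the same in 2.1.1 and 2.1.5, and the Protocol leaves all analysis detail to the SAP. The conflicting Subgroup 3 text governs descriptive tables only. Entry runs through the eCRF rule, and the core laboratory confirms eligibility.

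Much of this stands, and it rules out several stronger readings.

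- **A reader might infer that a fetus with septal restriction alone has no efficacy result anywhere.** The documents do not support that. SAP 2.1.1 promises a separate analysis and the Subgroup 3 label covers the case. PP_ENR (SAP 2.1.3) also states no high-risk exclusion, and the primary variable is analysed on PP_ENR. As worded, the fetus counts there, though pooled with all others.
- **A reader might infer two rival primary populations.** Within the SAP there is one removal rule. The discrepancy is between that rule and the Protocol's separate-group text, and between that rule and SAP 4.6.3.
- **A reader might extend the A2 conflict to restrictive septa, or to the primary result.** A restrictive septum can still shunt left to right, and the intact case never reaches FAS_ENR. Inconsistent enrolment between sites is possible but speculative.

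These arguments do not rescue SAP 4.6.3. The label and the text after it describe different sets, and the population named for the tables contradicts both the label and the promise in 2.1.1.

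**Conclusion.** The point holds as a set of internal contradictions that should be corrected before the analysis. Three of the seven high-risk combinations do not fit the Subgroup 3 text, so its claim to equal the high-risk population is false as written. Septum alone is covered by the label only. Followed literally, the tables meant to report high-risk fetuses contain none of them. The intact-septum conflict with A2 is real but narrow: it affects whether such a fetus counts as high-risk or as an erroneous inclusion, and not FAS_ENR.

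The numerical effect is unknown, because neither document gives the expected share of any of these classes. The conclusion assumes that severe MR together with severe LA enlargement forms one condition in SAP 2.1.5, which the opening wording of that section supports. It also rests on the text alone, since the analysis-set diagrams (SAP Figures 5 and 6) could not be read. A separate high-risk branch there would not change the wording of 4.6.3 or the table titles.

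**What to change.** 1. Use one high-risk definition, read at inclusion, in Protocol Exclusion criteria, Protocol subgroup c, and SAP 2.1.1, 2.1.5 and 4.6.3, so that Subgroup 3 is exactly the set removed from FAS_ENR. Settle the severity terms for LA enlargement and for septal restriction at the same time. The choice of definition is the sponsor's. Because any departure from SAP 2.1.5 alters FAS_ENR, it should be made and dated before outcomes by group are seen.
2. Tabulate Subgroups 2 and 3 on the high-risk population, once for all enrolled and once for live-born, in place of FAS_ENR and FAS_BIRTH. Retitle Tables 2.4.1.2, 2.4.1.3, 2.4.2.2 and 2.4.2.3 to match.
3. Reconcile A2 with the intact-septum wording in Protocol Exclusion criteria and SAP 2.1.1, 2.1.5 and 4.6.3. Which eligibility rule should apply is for the sponsor to decide.

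The cost is rewording of both documents and four table titles. This assumes that the annotated eCRF already records MR, LA size, septal status and hydrops at baseline. SAP 2.1.5 needs them there, but SAP 3.1 lists only potential confounders and refers to the eCRF for the rest.

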2.1.6 Safety Population

All enrolled fetuses will be included in the safety population, also those wrongly included if such cases will exist.

Figure 5. Full analysis sets (FAS)

ToP=Termination of Pregnancy; IUD=Intrauterine Death; GW=Gestational Weeks; FAS=Full Analysis Set; FAV=Fetal Aortic Valvuloplasty

STATISTISKA KONSULTGRUPPEN	Statisti	cal Analysis Plan
Protocol: Effect of fetal aortic valvuloplasty on outcomes	Protocol No):
	Version: 1.0	Page 14 of 26

Figure 6. Per protocol populations (PP)

ToP=Termination of Pregnancy; IUD=Intrauterine Death; GW=Gestational Weeks; PP=Per Protocol; FAV=Fetal Aortic Valvuloplasty

Figure 7. Safety population

GW=Gestational Weeks; FAV=Fetal Aortic Valvuloplasty

3 STUDY VARIABLES

3.1 Fetal and Pregnancy Variables

The following characteristics regarding the pregnancy and the fetus will be collected at inclusion and baseline fetal echo:

- Gestational age at primary diagnosis (weeks and days) (potential confounder)
- Year of diagnosis (potential confounder)
- Primary diagnostic hospital, city and country

Statistical Analysis Plan

Protocol No:

Effect of fetal aortic valvuloplasty on outcomes

- Average yearly case volume of center performing fetal intervention (potential confounder)
- Gestational age at baseline fetal echo (weeks and days) (potential confounder)
- Hospital, city and country where each echo was performed
- Maternal age
- Parity

Protocol

- Multiple pregnancy (potential confounder)
- Mother's body mass index (BMI) (potential confounder)
- Maternal comorbidities
- Maternal contraindications to fetal intervention
- Echo data (baseline fetal echo). Only those considered as potential confounders listed here (for a full set of variables for all three echoes, 2 fetal and 1 neonatal, please see the annotated eCRF):
 - Left ventricular end-diastolic diameter (mm and z-score) (potential confounder)
 - Left ventricular inlet length in diastole (mm and z-score) (potential confounder)
 - Mitral valve diameter, 4 ch view in end diastole (potential confounder)
 - Aortic valve annulus diameter (mm) (potential confounder)
 - Mitral valve inflow pattern (Biphasic; Fused; Monophasic; No inflow) (potential confounder)
 - LV:RV inlet length ratio (potential confounder)

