1.2 Study Design

The study is an international multicenter prospective observational cohort study with a comparison cohort. Included are fetuses with a diagnosis of aortic stenosis who satisfy inclusion/exclusion criteria between 23+0 and 31+6 weeks of gestation. The decision whether a fetal balloon dilatation shall be attempted is not part of the study protocol. The number of examinations of mother/fetus/infant in this study is not different from the number of examinations that will be recommended for someone choosing not to be part of this study. The participation in the study is not affecting the treatment mothers and fetuses are receiving during pregnancy, nor how the infant is examined and treated after birth. The aim of the study is to, in a prospective and organized way, collect and evaluate multi-center data in order to reduce the risk for selection bias, missing data and inter-variability between participating centers.

Cases will be recruited from centers offering fetal aortic valvuloplasty and and from centers not offering this treatment. All intervention cases will be recruited from high volume

Protocol

Statistical Analysis Plan

Effect of fetal aortic valvuloplasty on outcomes

1.0

intervention centres which have performed at least 20 fetal cardiac interventions during the last five years before including the first case in the study. Fetal and postnatal echocardiographic examinations will be reviewed and remeasured by a core laboratory to confirm eligibility for inclusion, and identify potential measurement errors.

Data from two fetal echoes and one postnatal will be collected and each contains a comprehensive set of two-dimensional and Doppler measurements which will enable analysis of cardiac growth and development during pregnancy. Analysis of change of dimensions of the left heart structures and selected hemodynamic variables from the point of study inclusion until just before the first postnatal catheter or surgical procedure provides an opportunity to make a comparison between the groups that is unbiased with respect to centerspecific postnatal treatment policies. Three echocardiographic examinations and a 2-year follow-up regarding patient outcome will be performed as per Figures 1-3 below.

Figure 1. Study Overview – Fetal Protocol

STATISTISKA KONSULTGRUPPEN	Statistic	cal Analysis Plan
Effect of fetal aortic valvuloplasty on outcomes	Protocol No:	
	Version: 1.0	Page 8 of 26

Figure 2. Study Overview – Neonatal Protocol

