1.4 Study Groups

The main analysis comparing intervention versus non-intervention will be on an intention-totreat, i.e. intention to perform fetal aortic valvuloplasty, basis. Intention to perform fetal valvuloplasty is defined as being present if the needle has been introduced through the maternal abdominal wall even if the fetal thorax has not been touched. Subjects will be Protocol

Statistical Analysis Plan

1.0

identified as belonging to the fetal aortic valvuloplasty (FAV) or the no-FAV groups as listed below.

The following groups will be identified:

- Subjects that undergo a technically successful fetal aortic valvuloplasty at a high volume intervention centre (FAV 1).
- Subjects with intention-to-treat (according to the above definition) at a high volume intervention centre but with no technical success (FAV 2).
- Subjects counselled at a center not performing or referring for fetal aortic valvuloplasty (no-FAV 1).
- Subjects counselled at a high- or low-volume intervention center, or at a center offering referrals to a center performing interventions, and the parental decision is to not perform fetal aortic valvuloplasty (no-FAV 2).

The main analyses will be to compare FAV 1+2 versus no-FAV 1+2. The expected proportion of enrolled fetuses/infants will be 2 [FAV] : 1 [no-FAV]. Complementary analyses will be comparing FAV 1 versus no-FAV 1, and FAV 1 versus no-FAV 1+2.

Figure 4. Main and complementary analysis

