4 STATISTICAL METHODOLOGY

4.1 General Methodology

Continuous variables will be described by means, standard deviation (SD), median and range, and categorical by number and percentages.

Main analyses will be performed comparing FAV 1+2 versus no-FAV 1+2 groups on FAS_{ENR} population. Complementary analyses will be performed on FAS_{BIRTH}, PP_{ENR} and PP_{BIRTH}. Separate descriptive comparisons between FAV 1 vs no-FAV 1 and FAV 1 vs no-FAV 1+2 groups will also be performed.

Comparisons between the two groups with respect to demographics and baseline characteristics and safety data will be performed using Fisher's exact test for dichotomous variables, Mantel-Haenszel Chi-square test for ordered categorical variables, Chi-square test for non-ordered categorical variables, and Fisher's non-parametric permutation test for continuous variables.

Due to the non-randomised design, all analyses will be adjusted for confounders. It is important that all known confounders at the time of inclusion are defined. The main confounders will be gestational age at first diagnosis and at inclusion, morphology and hemodynamics of the fetal heart at the time of study inclusion and possibly some data about the mother's health which could have an impact on the chance of success with fetal intervention, such as BMI. Although the study is designed to minimize bias by using strict echocardiographic inclusion criteria, it will be necessary to analyse the groups at baseline carefully with respect to a number of selected echocardiographic variables describing the size and function of the left heart. If this analysis shows that, in spite of the strict inclusion criteria, there are significant differences between the groups regarding data that are at the same time risk factors for the studied outcomes the analyses will be adjusted for those additionally defined confounders besides the known ones. A sensitivity analysis will also be performed for the primary variable applying propensity score matching procedure (1:1 or 2:1 if possible) including all variables that are of importance (p<0.10 using logistic regression) for discrimination of FAV vs no-FAV group and those identified/known confounders in the adjusted analyses.

Known confounders are:

• Gestational age at primary diagnosis (earlier gestational age could indicate more severe disease, and might differ between countries and centres due to different

Protocol

Statistical Analysis Plan

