Effect of fetal aortic valvuloplasty on outcomes

Protocol No:

screening policies) and gestational age at inclusion. Most probably they are highly correlated and in that case the more influential of the two will be used.

Variables listed under 3.1 as potential confounders will be investigated whether they are important for discriminating FAV vs no-FAV and whether they are confounders (associated p<0.10 both to the group and the outcome).

Dichotomous outcome variables will be analysed using logistic regression, adjusted for identified confounders available at the time of study inclusion. Odds-ratios (OR) with 95% confidence intervals (CI) will be presented.

Time-to-event analyses will be performed using Cox proportional hazards models adjusting for identified confounders. Proportional hazards assumption will be checked by visually reviewing log(-log(survival)) vs log(time) graphs, and by adding interaction between treatment group and log(time) in the model, where significant interaction indicates non-proportionality. Other methods will be applied, e.g. Poisson regression for time varying data, allowing study of changes in treatment effects over follow-up time, in case non-proportionality of hazards occurs.

Time-to-event data will be described by using Kaplan-Meier technique.

The primary analyses for the FAV vs no-FAV group conducted on FAS_{ENR} population will be considered as confirmatory analyses and a total significance mass of 0.05 will be applied. The tests will be performed on the primary variable and the most important secondary variables using fix sequential testing procedure according to the following order:

1. Primary variable: Transplantation-free survival from fetal diagnosis to 2 years postnatal age, having a biventricular circulation without pulmonary hypertension at that time

2. Secondary variable: Transplantation-free survival from fetal diagnosis to 2 years of age

3. Secondary variable: Survival from fetal diagnosis to live birth at term (≥37 weeks)

4. Secondary variable: Proportion of included fetuses who have a biventricular circulation at neonatal hospital discharge

5. Secondary variable: Proportion of included fetuses who have a biventricular circulation at 2 years of postnatal age

This means that first test must be significant on 0.05 significance level in order to be able to further confirm the tests 2 to 5, and the second test must be significant on 0.05 level in order to be able to confirm tests number 3 to 5, etc.

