4.6 Efficacy Analyses

4.6.1 Primary Efficacy Analysis

Primary efficacy analysis, test between FAV vs no-FAV regarding transplantation-free survival from fetal diagnosis to 2 years postnatal age, having a biventricular circulation without pulmonary hypertension at that time, will be performed using logistic regression adjusted for confounders identified according to the section General Methodology above. OR with 95% CI will be presented. The primary analysis will be performed on FAS_{ENR} population and will compare FAV 1+2 versus no-FAV 1+2. This analysis will be included in the evaluation of the confirmatory tests. Complementary analyses will be performed on FAS_{BIRTH}, PP_{ENR}, PP_{BIRTH} populations, and on all populations comparing FAV 1 with no–FAV 1 and FAV 1 vs no-FAV 1+2.

Sensitivity analyses will be performed using Fisher's exact test comparing the FAV group with the matched no-FAV group obtained applying propensity score matching according to the description in General Methodology above, both on FAS and PP populations.

Vertical bar charts will be presented for graphical purpose.

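### Intervention-centre volume is flagged as a potential confounder although it is part of the exposure; if it enters the primary model or propensity score, most of the power or all of the matches can be lost

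*SAP*

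**What the plan says.** SAP 3.1, among the variables collected at inclusion and baseline fetal echo, lists "Average yearly case volume of center performing fetal intervention (potential confounder".

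SAP 4.1 then says "Variables listed under 3.1 as potential confounders will be investigated whether they are important for discriminating FAV vs no-FAV and whether they are confounders", with the criterion "associated p<0.10 both to the group and the outcome". Under SAP 4.6.1 the confirmatory analysis "will be performed using logistic regression adjusted for confounders identified according to the section General Methodology above". For the propensity-score sensitivity analysis, SAP 4.1 describes a matching model "including all variables that are of importance (p<0.10 using logistic regression) for discrimination of FAV vs no-FAV group", plus the confounders already identified.

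Two other sections fix what the volume variable looks like in each group. SAP 1.2 draws all FAV cases from "intervention centres which have performed at least 20 fetal cardiac interventions during the last five years". SAP 1.4 defines one control group as "Subjects counselled at a center not performing or referring for fetal aortic valvuloplasty (no-FAV 1", and SAP 1.5 expects this to be the larger control group.

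Neither document says how volume is coded for controls, restricts it to the FAV group, or keeps it out of either model.

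**The concern.** A confounder must be definable for every subject without reference to the treatment received. The volume of the centre performing the intervention is not: it comes into existence with the intervention. Every FAV fetus has a value from a centre averaging at least 20/5 = 4 procedures per year when it joined the study. A no-FAV 1 fetus has no such centre. A no-FAV 2 fetus may have been counselled at an intervention centre, but no centre performed an intervention on it.

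Volume therefore carries almost the same information as treatment group. If the screen admits it, the primary model has to separate two nearly identical columns, and the propensity score predicts treatment from a consequence of treatment. At stake are the precision of the confirmatory odds ratio and the feasibility of the only named sensitivity analysis for the primary endpoint.

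**Working it through.** **Inputs.** From SAP 1.5: 100 FAV, 50 no-FAV, success 60% versus 30%, two-sided alpha 0.05. From SAP 1.2: at least 20 interventions in five years. The documents give no distribution of volumes and no coding for controls, so both are assumed and varied.

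**1. The plan's own figure.** Full enumeration of the two-sided Fisher test gives 92.7% (stated 91.8%), and 98.9% for 100 versus 100 (stated 98.7%). Both are close enough to count as reproduced.

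**2. Logistic model without volume.** Expected cells are 60/40 and 15/35. SE(log OR) = √(1/60 + 1/40 + 1/15 + 1/35) = √0.1369 = 0.370. The log odds ratio is ln 3.5 = 1.253. Approximate power is Φ(1.253/0.370 − 1.96) = Φ(1.43) = 92%; simulation gives about 94%.

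**3. Volume added, controls coded 0.** The treatment coefficient now compares controls with FAV extrapolated down to a volume of zero. With mean volume m and variance s² in FAV, and no true volume effect:

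Var(log OR) = 1/(50×0.3×0.7) + 1/(100×0.6×0.4) + m²/(24 s²) = 0.1369 + m²/(24 s²).

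| Assumed FAV volumes per year | m | s² | m²/(24 s²) | SE | Power by formula | Simulated SE; power |
|---|---|---|---|---|---|---|
| uniform 4-20 | 12 | 21.3 | 0.281 | 0.65 | 49% | 0.66; 50% |
| uniform 4-10 | 7 | 3.0 | 0.681 | 0.90 | 28% | 0.92; 29% |
| equal shares of 4, 8, 12, 16, 20 | 12 | 32 | 0.188 | 0.57 | 59% | 0.58; 60% |
| equal shares of 4, 6, 8, 10 | 7 | 5 | 0.408 | 0.74 | 40% | 0.75; 39% |
| equal shares of 8, 10, 12 | 10 | 2.67 | 1.563 | 1.30 | 16% | 1.33; 15% |

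The simulated power lets volume enter only when it passes the p<0.10 screen. In the three equal-share rows it passed in 86-96% of trials, with the group half tested by a mean comparison. The median adjusted odds ratio in those rows was 3.5-3.6, so the harm is lost precision. The less FAV centres differ in volume, the larger the loss.

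**4. If outcome truly improves with volume.** The extrapolation then also shifts the estimate. For an assumed log odds ratio d per extra case per year, the treatment coefficient is about 1.253 − d×m. With m = 12: d = 0.05 gives exp(0.653) = 1.92, and d = 0.10 gives exp(0.053) = 1.05. Simulation agrees (1.92 and 1.05), with power of about 20% and 3%.

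**5. Some controls given a volume.** If 30% of controls carry their counselling centre's volume, collinearity weakens and power is about 75-82%; repeat runs under similar assumptions went down to 71%.

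**6. Propensity score.** With controls at 0 and every FAV case above 0, volume separates the groups completely. In the check, fitted scores were about 1 for FAV and about 0 for controls, so no pair can be matched.

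**7. Controls left missing.** On the literal reading, a complete-case model containing volume keeps 100 FAV and 0 controls, and the treatment effect cannot be estimated.

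**8. Would volume pass the group screen?** With controls at 0, the likelihood-ratio statistic for volume against group is −2[100 ln(2/3) + 50 ln(1/3)] = 190.95, p below 1e-40. Under the same separation the Wald p-value from logistic regression was 0.998 or higher. A likelihood-ratio or permutation test admits volume; a Wald test does not.

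**The case against.** The strongest reply is that the plan may never put volume into a model.

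- The SAP says candidates will be investigated, not that they all enter. SAP 4.1 names logistic regression for the propensity screen, and a Wald test there would reject volume under complete separation. This stands as far as it goes. But the test for the confounder screen is not named, and SAP 4.1 uses a permutation test for group comparisons of continuous baseline variables, which would admit it. A variable so identified would also go into the propensity score.
- If every control is missing, no group p-value can be computed, so volume cannot qualify. This also stands. The missing-value route does damage only if some no-FAV 2 fetuses are assigned a volume; a complete-case model would then drop all of no-FAV 1.
- SAP 4.1 limits adjustment to confounders available at inclusion. That could be read as a guard, but SAP 3.1 places volume among the data collected at inclusion and baseline echo, so it does not clearly exclude it.

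A reader might also infer that adjusting for volume would by itself erase the treatment effect. The figures do not support that: without a true volume effect the odds ratio stays near 3.5.

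A reader might further infer that the p<0.10 screen as such leaves serious residual confounding. With six independent confounders of assumed strength, the median odds ratio under the null was about 1.2, with type I error of 7.3-7.9% against 5.9-6.4% for a fixed covariate set. The bias largely disappears when covariates correlate at 0.3, which is plausible for several measurements of one left heart. SAP 4.1 also treats gestational age as a known confounder, outside that screen.

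**Conclusion.** The point holds for centre volume. The SAP as written permits a component of the exposure to enter the confirmatory model and the propensity score, and nothing in either document clearly prevents it.

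If controls are coded 0 and volume enters, power at the planned size falls from about 94% to about 29-50% for assumed volumes spread over 4-10 to 4-20 per year. The equal-share volume sets in the table widen this to 15-60%. The estimate itself is pulled toward 1 only if outcome improves with volume. With the same coding, a propensity score containing volume allows no matches.

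The structural defect is certain from the text. The magnitudes rest on assumed volumes and coding, and entry depends on the unstated group test. This should be corrected before database lock. The general p<0.10 selection rule is a secondary matter and does not carry the point.

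**What to change.** In SAP 3.1, delete the potential-confounder label from intervention-centre volume. In SAP 4.1, add a sentence such as: *Volume of the intervention centre is a characteristic of the exposure. It will not be a candidate for the adjusted models or the propensity score, and will be used only descriptively or as an effect modifier within the FAV group.* If adjustment for centre experience is wanted, define a centre variable that exists for every fetus and fix its coding before database lock.

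The cost is SAP wording only. No data collection changes, and volume can still be reported for the FAV group.

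Optional and secondary: pre-specify the baseline fetal covariates instead of selecting them by p<0.10, and use the same list in the propensity score. Keep the SAP's rule on gestational age at primary diagnosis or at inclusion, and give a reason for any other flagged variable that is dropped. With 0.6×100 + 0.3×50 = 75 successes and 75 failures expected, about 7-9 parameters are affordable.
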